5.3.2 Masking Procedures

The interventions will not be masked in this study. Group randomization is being performed in this study in order to minimize cross-contamination of the intervention conditions. Outcome data from the trial will be reviewed centrally by a Data and Safety Monitoring Board for the ECC Consortium. The dental hygienists who screen the children to capture caries outcomes annually will be blinded to the intervention condition, and study investigators will be masked to the final study outcomes, findings, and results until the study is completed.

5.3.3 Reasons for Withdrawal

Children may be withdrawn from the study if they have an adverse reaction to the FV, or any other aspect of the study. They will also be withdrawn if informed consent is withdrawn by the parent/caregiver.

5.3.4 Handling of Withdrawals

If a child withdraws from the study because of an adverse reaction to the FV, it will be requested that the child continue in the evaluation but not the treatment part of the study (i.e., the annual oral health screening, parent education and child classroom sessions, and parent/caregiver questionnaires related to dental knowledge, attitudes, and behavior). This will be done in an attempt to obtain as complete data as possible in follow-up. Of course, if the parent/caregiver wants to withdraw the child from the study entirely, those wishes will be honored.

5.3.5 Termination of Study

The study will be terminated in the field after the intervention and subsequent follow-ups have been completed and the data are completely cleaned and transferred to the investigator's site. The study will be terminated at the investigators' site when all data analyses and study manuscripts have been completed. The central Data and Safety Monitoring Board will be monitoring the safety and efficacy data at intervals specified by them throughout the study, and they have the authority to terminate the study earlier on the basis of these data reviews.

NIDCR, as sponsor, will also be monitoring the study conduct and can recommend termination for cause.

6 STUDY INTERVENTION/ INVESTIGATIONAL PRODUCT

6.1 Study Product Description

6.1.1 Acquisition

The FV will be purchased from 3M (formerly Omnii Oral Pharmaceuticals). The FV will be shipped to the University of Colorado, School of Dental Medicine and forwarded from there to the field office sites.

6.1.2 Formulation, Packaging, and Labeling

The trade-name of the FV is VANISH; it is a 5% Sodium Fluoride white varnish. It is packaged in 0.5ml unit dose packets and applicator brushes. The clearly labeled box contains 1000 sealed unit doses, patient instructions, and dosage stickers to measure quantity dispensed.

6.1.3 Product Storage and Stability

For both intervention conditions, the FV will be labeled and stored in a secure locked office, and out of reach of the children. The FV is a stable agent but is potentially a flammable liquid, so it is recommended that it be stored away from heat, acids, and oxidizing agents. The product MSDS does not provide a recommended storage temperature; we will therefore store it in a climate-controlled, temperature-monitored area between 10°C - 32°C. Handling instructions caution that the product is to be kept away from heat, sparks, open flame, pilot lights and other sources of ignition; avoid breathing vapors, mists, or spray; use general dilution ventilation and/or local exhaust ventilation to control airborne exposures; avoid eye contact; avoid prolonged or repeated skin contact; and recommend the washing of hands after handling and before eating. The product's MSDS is attached to this protocol (*Appendix A*).

6.2 Dosage, Preparation and Administration of Study Intervention/Investigational Product

Only trained study staff will apply the FV to the teeth of the children whose parents have consented. Aseptic procedures and universal precautions will be maintained at all times. Study records and HS child health records will document the application of the FV. Consistent with CDC Advisory Committee on Immunization Practices and standards of pediatric practice, COHSs will observe the child(ren) for a minimum of 15 minutes following the fluoride varnish

application to observe, resolve, and report any untoward effects. Parents will be provided with post-fluoride instructions each time the FV is administered.

Dosage guidelines include the following:

- a. 0.25 mL dosage for children with primary dentition only, or to treat any child requiring limited tooth surface or cavity area coverage
- b. 0.40 mL dosage for children with mixed dentition who require extensive tooth surface or cavity area coverage
- c. 0.50 mL dosage for children with permanent dentition who require extensive coverage.

Directions for administration are:

1. Treatment areas should minimally be “toothbrush” clean; a prophylaxis is not required.
2. Peel the foil pouch open to expose the VANISH unit-dose package and applicator brush.
3. Tear off the end of the unit-dose package and dispense the entire contents onto the dosing guide.
4. Use the applicator brush to thoroughly mix VANISH, since the components of all sodium fluoride varnishes can separate during storage. While mixing, keep the material evenly distributed inside the inner circle of the dosing guide.
5. Use the dosing guide to determine the amount of VANISH required.
6. For best results, excessive saliva is removed by blotting the tooth surfaces with gauze. Avoid passing applicator brush through pooled saliva to prevent premature setting on bristles.
7. Paint VANISH evenly to the areas being treated.
8. Consistent with CDC Advisory Committee on Immunization Practices and standards of pediatric practice, the COHSs will observe the child(ren) for a minimum of 15 minutes following the fluoride varnish application to observe, resolve, and report any untoward effects.
9. It is best for the patient to keep VANISH in contact with tooth surfaces as long as possible, minimally for 4 hours. During the treatment period, the patient and the parent/caregiver should be instructed to avoid hard foods, brushing teeth, and use of products containing alcohol (beverages, oral rinses). A thorough brushing and flossing will remove excess VANISH from tooth surfaces following the treatment period.

6.3 Modification of Study Intervention/Investigational Product for a Participant

No modifications of the FV will be made.

6.4 Accountability Procedures for the Study Intervention/Investigational Product(s)

Study staff involved in the delivery of the FV will be required to sign out the inventory prior to use. The field office will maintain records of FV units in the inventory and signed out to the study personnel. Lot numbers and expiration dates of the product will also be tracked. Unopened packages and expired fluoride varnish will be returned to the NNFO, where investigators will determine the method of disposal.

6.5 Assessment of Subject Compliance with Study Intervention/Investigational Product

Records of the FV applications and post application observation will be kept for each child in the COHS intervention group as a record of compliance with the intervention. A copy of this information will be placed in the child's Head Start Health Record. Data will be collected on the dental service utilization of each child in the study at the time of the annual ACASI survey measures completed by parents (objectives 3.1.2.2 and 3.1.2.3/ outcome 3.2.2.2 and 3.2.2.3).

6.6 Concomitant Medications/Treatments

Children taking fluoride supplements should discontinue the use of the supplements for 2-3 days following each FV application.

7 STUDY SCHEDULE

7.1 Screening

Children and parents will be screened for entry into the study according to inclusion/exclusion criteria at the time of enrollment.

7.2 Enrollment

Once the HS programs that will participate in the two treatment arms have been identified, study staff will travel to each participating site and host sessions for teachers, staff and parents to explain the program and begin obtaining informed consent from parents. Upon obtaining informed consent from a parent/legal guardian, the child will be enrolled in the study, along with his/her parent/primary caregiver, who also will provide informed consent. A baseline oral health screening will be completed, along with the ACASI survey completed by the parents/caregivers regarding demographic information about the children, health history, and the parents'/caregivers' dental knowledge, attitudes, and behaviors. Toothbrushes and toothpaste will be given, enough for each family member in the household.

Prior to the varnish dates, under normal and usual conditions, notices will be sent home with children notifying parents of the upcoming varnish date(s) for the COHS intervention group. The notice will state the date(s) that the COHS will be administering FV in the HS classroom.

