Description of Agent or Intervention:	Intervention will include application of fluoride varnish (FV) offered offered 4x a year and oral health promotion (OHP) and education for 2 years.
Objectives:	
Primary:
 
1) To develop, with input from tribal/community members, a manualized intervention protocol for an early childhood caries (ECC) prevention program to be delivered by specially trained community paraprofessionals, called Community Oral Health Specialists (COHS)2) To implement and evaluate the delivery of FV and OHP programs in American Indian (AI) Head Start Centers (HSCs) under the following conditions: Group #1—FV offered 4x a year and OHP for 2 years provided by COHS Group #2— Usual oral health care made available by the IHS Dental providers (or other usual providers)3) To assess efficacy by comparing decayed, missing, and filled

primary tooth surfaces (dmfs) over time between the 2 groups.

Secondary:

- 1) To assess specific caries patterns
- 2) To investigate moderators/mediators of the intervention conditions as ascertained via questionnaires on oral health knowledge, attitudes, and behaviors
- 3) To investigate participant utilization of medical and dental services for oral health problems and intervention costs, intervention savings, net intervention costs, costs/net costs per participant, costs/net costs per unit decrease in caries associated with each intervention condition

[figure not shown]
**Description of Study
Design:**

The study design will be a cluster randomized design. HSCs within the Navajo Nation (NN) will be stratified by population size and randomized within strata to the two groups. All children within the HSC classrooms and a parent/primary caregiver of each child will be invited to participate in the intervention condition to which the HSC is randomized. Children will participate after informed consent by the parents and after informed consent by the participating parent/primary caregiver for her/himself. To be consistent with NIDCR, we will count the child and participating parent/primary caregiver dyad as one enrolled participant (unit). Baseline and annual measures of dmfs and of dental knowledge, attitudes, and behavior will be collected. Changes in these outcome measures will be compared between the two groups.

**Estimated Time to
Complete Enrollment:**

6 months for each intervention year (year 1 and year 2)

Schematic of Study Design:

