5 STUDY ENROLLMENT AND WITHDRAWAL

5.1 Subject Inclusion Criteria

Once the HSCs on the Navajo reservation are selected for the study, the HSC will be randomized to the two intervention groups. Subject inclusion criteria include:

- A) Children ages 3-6 years at the time of enrollment in the Navajo reservation HSCs and having a primary caregiver (preferably parent, or the child's legal guardian as documented by the HSC, but another caregiver such as an aunt or grandmother will not be excluded if he or she is the primary caregiver for the child). A parent or legal guardian must be available to give consent for the child to participate in the study. (Note: multiple children from the same family will not be excluded, provided each child is enrolled in the Navajo Head Start Program.)
- B) American Indian, as defined by the tribe, or children of other races/ethnic groups who are in the HS classes on the Navajo reservation (the numbers in this latter group are expected to be very small); and
- C) Parent/caregiver able to read, understand, and sign a consent form for his or her own participation, and willing and able to follow study procedures and instructions.

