5.2 Subject Exclusion Criteria

A child will be excluded if he/she has any of these conditions:

- A) Allergy to any of the components of the FV (for children attending HSCs in Group 1)
- B) Ulcerative gingivitis, stomatitis or other conditions resulting in chronically disrupted or irritated oral mucosa (for children attending HSCs in Group 1)
- C) Any other conditions or findings that, in the opinion of the investigator, would interfere with or preclude participation in the study in either Group 1 or Group 2.

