13.3.1 Informed Consent/Assent Process (in Case of a Minor)

Parents/legal guardians will be asked to provide consent for their children (by definition younger than 7 at enrollment), whether or not they themselves will participate in the study activities. The parent/legal guardian will be advised about procedures in the relevant arm of the study and informed that they may discontinue the child's participation at any time, including any time that they may sense that their child wishes to discontinue.

A parent age 15 or older who has not her or himself attained the age of majority and wishes his/her HS child to be enrolled in the study may provide consent for that child without further documentation (COMIRB instructions for Attachment H). Time and care will be taken to assure that underage parents understand their and their children's roles.

A parent age 15 or older who has not her or himself attained the age of majority and does not provide documented proof of emancipation granted by state or tribal authority must, however, obtain his or her own parent's consent to participate in the study as parent/caregiver. The underage parent's assent to participate in the study her or himself will be documented on the consent form; the same consent form will be used to document the full informed consent of her or his parent.

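### Families are consented after their centre's arm is set, with arm-specific information, so who enrols could differ by arm; size and direction are unknown

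*Combined protocol and SAP*

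**What the plan says.** The order of events has to be put together from several sections of the protocol.

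- **Allocation.** Section 5.1: "Once the HSCs on the Navajo reservation are selected for the study, the HSC will be randomized to the two intervention groups".
- **Approach and consent.** Section 7.2: "Once the HS programs that will participate in the two treatment arms have been identified, study staff will travel to each participating site". There they host sessions to "explain the program and begin obtaining informed consent from parents". The baseline oral health screening and caregiver survey come after consent in the same section.
- **Invitation.** The Protocol Summary (Description of Study Design) says that all children in the classrooms, with a caregiver, "will be invited to participate in the intervention condition to which the HSC is randomized".
- **Information given.** Section 13.3.1: "The parent/legal guardian will be advised about procedures in the relevant arm of the study".
- **Masking.** Section 5.3.2: "The interventions will not be masked in this study". The same section blinds the annual screening hygienists to condition and keeps investigators from the final results. It says nothing of the kind about families or the staff who recruit them.
- **Eligibility.** Section 5.2 confines two child exclusions to Group 1: allergy to a varnish component, and conditions that chronically disrupt the oral mucosa.
- **Timing.** Section 4 gives a six-month enrolment window in each of years 1 and 2.

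**The concern.** Randomising HSCs balances the HSCs and the pool of children attending them. It does not balance the subset whose parents later agree to join. If parents know their arm when they decide, the decision can depend on it. The two offers differ: Group 1 gets in-school varnish and health promotion, while Group 2 gets screening, surveys and supplies alongside usual care. The Group 1-only exclusions are a second route to different enrolled groups, even if consent behaviour is identical, though the number of children affected may be small.

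At stake is whether the two sets of enrolled children are comparable in caries risk and in family motivation. Adjustment for baseline dmfs deals with measured caries. It does not deal with home hygiene, care-seeking or motivation that differ at the same baseline dmfs and go on to affect the increment. A larger sample does not remove a bias of this kind, and blinded screening protects the measurement, not the recruitment.

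**Working it through.** **Sequence.** On its own, the section 7.2 sentence could be read as meaning only that sites have been chosen. Sections 5.1 and 13.3.1 and the Protocol Summary rule that out: HSCs are randomised on selection, the invitation is to the allocated condition, and the advice is about the relevant arm. The order is therefore allocation, then approach and consent with arm-specific information, then baseline screening. That recruiting staff know the arm is an inference from these sections and section 5.3.2, but a close one. The documents describe no list of families made before randomisation, no recruiter kept unaware of arm, no log of children approached against enrolled by arm, and no analysis of enrolment differences.

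**Direction.** Let g be the mean dmfs of non-consenters minus that of consenters (taken as equal in both arms), and p1 and p2 the consent proportions. The enrolled mean in an arm is the population mean − g(1 − p), so

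baseline gap (Group 1 − Group 2) = g(p1 − p2).

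If non-consenters have more caries (g > 0) and Group 1 consents more (p1 > p2), Group 1 starts with the worse baseline. If g is negative the sign reverses. If g = 0 or p1 = p2 the gap is zero. The documents give none of these three quantities.

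**Scale of a residual difference.** The plan has no figure of its own for this, so what follows is an illustration. Inputs from section 10.2:

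- 520 children per group and 70% retention: 520 × 0.70 = 364 analysed per arm. The 520 is taken as stated.
- Class size 20: 20 × 0.70 = 14 retained per class.
- Intraclass correlation 0.045: design effect = 1 + (14 − 1) × 0.045 = 1.585.
- SD 24 and type I error 0.05, taken as two-sided because the alternative is stated as a difference.

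SE of the difference = 24 × √(2 × 1.585 / 364) = 2.24 surfaces.

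With no true effect and a residual arm difference b left after adjustment,

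false-positive rate = 1 − Φ(1.96 − b/SE) + Φ(−1.96 − b/SE).

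| Assumed residual b (surfaces) | b/SE | Two-sided false-positive rate |
|---|---|---|
| 0 | 0 | 5.0% |
| 1 | 0.45 | 7.3% |
| 2 | 0.89 | 14.5% |
| 3 | 1.34 | 26.8% |

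The values of b are assumptions; nothing in the documents supports one over another. The SD of 24 is that of unadjusted dmfs. A smaller SE after baseline adjustment would make the same b do more harm, and a larger SE from multi-class HSCs would make it do less.

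**The case against.** The case on the other side is substantial.

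- Every child in the classrooms is invited (Protocol Summary), which limits selection by recruiters. It does not equalise uptake by families.
- Usual-care families are not offered nothing. Section 2.3.2 gives them toothbrushes and toothpaste after each annual survey, section 7.2 gives supplies for the household at enrolment, and section 2.3.2 describes the screening as a service not always available. This narrows the contrast in incentives without removing it.
- The outcome is change from baseline, and section 10.4 describes baseline as a covariate. This handles measured caries, although that section calls the practice customary and does not fix the primary model.
- Caregiver knowledge, attitudes and behaviours are collected at baseline (section 7.2), and section 10.4 adds sociodemographics and such variables in secondary models. Motivation is thus partly measured, but those models are secondary and meant to explain the effect.
- Section 13.3 says the consent forms describe the varnish and health promotion in detail, so the written wording may already be common to both arms. Appendix C and the Manual of Procedures are not available to settle this. The arm-specific invitation and advice remain.

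A reader might infer that enrolment did differ, or that the bias must favour the intervention. The documents support neither: they contain no consent data, and the sign depends on unknown quantities. A reader might also set an assumed baseline dmfs gap against the planned effect of 9.6 surfaces (40% of 24) and call the ratio the bias. That would be wrong, because a baseline gap is the part the design measures and can adjust for; only what is left afterwards biases the comparison.

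**Conclusion.** The point holds as a statement of risk. The planned order, with arm-specific information and eligibility, leaves the enrolled children open to post-randomisation selection, and no other section closes that gap. The mitigations are real but partial, and unmeasured differences would remain.

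The size and direction cannot be estimated from the documents, and zero is possible. The false-positive rates of 7.3% and 14.5% show only what a residual of 1 or 2 surfaces would do under the section 10.2 assumptions. They do not predict that such a residual exists. The change is worth making because it removes a source of bias cheaply and leaves the sample size as it is.

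**What to change.** In section 7.2, have the data coordinating center withhold each HSC's allocation from field staff and families until first-year consent, eligibility assessment and baseline screening at that HSC are complete. Section 5.3.1 assigns each HSC by its own random digit, so releasing one allocation does not reveal another. Bring the Protocol Summary, section 5.1 and section 13.3.1 into line.

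- Use one consent script and one set of information describing both arms. Assess and record the section 5.2 criteria identically in both arms before allocation is disclosed.
- For children enrolled after their HSC's allocation is known, concealment is not possible. Use the same script in both arms.
- Report children approached, consented and excluded, together with baseline dmfs and caregiver measures, by arm and enrolment year. This is useful whether or not the order changes.
- If concealment is adopted, prespecify a sensitivity analysis restricted to children enrolled before their HSC's allocation was disclosed. Without concealment this analysis removes no recruitment bias, because first-year families are also consented after allocation.

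The cost is a reordering of steps and, depending on what the forms now say, a consent amendment. Scheduling of an HSC's first varnish visit waits for its baseline screening, and usual-care families hear about the varnish arm. The reporting needs a log of children approached.

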7.3 Follow-up Visits for FV

The applications of FV for HS children and OHP will be delivered in the HSCs by the COHS (Group 1). FV will be offered 4x a year for 2 years to children in the classroom on the scheduled day; multiple attempts will be made to provide FV to children not in the classroom on the scheduled day. Group 2 participants will receive usual oral health care made available by the IHS Dental providers (or other dental providers outside the reservation).

Annual dmfs measure of the children, and parent ACASI survey to collect dental knowledge, attitudes, and behaviors will take place annually for 3 years. We will follow the families whose children age out of Head Start and make arrangements for them to complete the child oral health screening and parent ACASI survey at a convenient time and location. All annual follow-up assessments will be done as near as possible to the anniversary of the previous year's oral health screening at that HSC, with the goal of completing them within a month either side of that date.

